Appendix 8 - Protocol for QTc Substudy

Evaluation of the Effect of Plitidepsin on Cardiac Repolarisation (QTc Duration) in Patients with COVID-19 Treated in Study APL-D-003-20

INTRODUCTION

Cardiac toxicity evaluation during preclinical/toxicology studies with plitidepsin did not suggest any potential clinically relevant cardiotoxicity risk in humans. A retrospective study of the cardiac adverse events (e.g., rhythm abnormalities, myocardial injury events, electrocardiogram [ECG] alterations) that occurred in patients (n=578) treated with single-agent plitidepsin was conducted. This study showed that the frequency of these events was not different from the frequency reported in the age-matched healthy population, thereby suggesting that plitidepsin- has a safe cardiac risk profile in cancer patients.¹

This QT corrected (QTc) substudy associated with clinical trial APL-D-003-20 will determine whether plitidepsin at 1.5 and 2.5 mg flat dose on Days 1 to 3 has any effects on the QT interval in patients with coronavirus disease 2019 (COVID-19).

Substudy Rationale

An undesirable effect of some drugs is their ability to delay cardiac repolarisation, which can be measured as a prolongation of the QT interval on the surface ECG. The QT interval represents the duration of ventricular depolarisation and subsequent repolarisation, and is measured from the beginning of the QRS complex to the end of the T wave.

A delay in cardiac repolarisation creates an electrophysiological environment that favours the development of cardiac arrhythmias, mostly TdP but possibly other ventricular tachyarrhythmias as well. TdP is a polymorphic ventricular tachyarrhythmia that appears on the ECG as a continuous twisting of the vector of the QRS complex around the isoelectric baseline. The TdP can degenerate into ventricular fibrillation, leading to sudden death. Documented cases of TdP (fatal and nonfatal) associated with drug use have resulted in the withdrawal of several drugs from the market and the relegation of others to second-line status.

In general, there is a qualitative relationship between QT prolongation and the risk of TdP, especially for drugs that cause substantial prolongation of the QT interval. Therefore, an adequate pre-marketing investigation of the safety of a new pharmaceutical agent should include rigorous characterisation of its effects on the QT/QTc interval.²

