Because of its inverse relationship to the heart rate, the measured QT interval is routinely corrected by several formulae to a less heart rate-dependent value, which is known as the QTc interval. Fridericia's correction method (QTcF)³ is considered the more accurate general method for heart rate correction.⁴ In certain cases, individual QT correction based on QT-RR relationship is a preferred method.⁵

Substudy Design Rationale

Patients with COVID-19 included in study APL-D-003-20 allows assessment in a Phase 3 clinical trial setting similar to that for which therapeutic use of plitidepsin is being evaluated. This substudy will be conducted at some of the sites participating in study APL-D-003-20.

Although the daily variability in QTc interval in these patients' setting has not been well described, it may be even larger because enrolled patients are likely to have advanced age or concomitant medical problems.⁶ For this reason, an intrapatient standard deviation of 30 milliseconds is assumed. To reduce intrapatient variability due to measurement error, it has been recommended that the baseline QTc be rigorously investigated and be expressed as the mean of multiple ECG assessments.⁷ For this purpose, 2 sets of triplicate ECG tracings recorded before plitidepsin administration will be considered baseline assessments: 1 set before and 1 set after prophylactic antiemetic medication administration.

Electrocardiogram assessments will be performed by means of continuous 12-lead ECG automated digital collection. All digital ECG continuous recordings will be sent to a third-party central ECG laboratory for measurement of intervals, diagnostics of abnormalities and review of ECG waveform morphology review. This will prevent the potential introduction of bias during the analysis of ECG recordings.

Samples for whole blood plitidepsin concentration measurement will be collected matching the clock times of ECG measurements, and are aimed at conducting a concentration QTc analysis.

OBJECTIVES

Based on the aforementioned scientific background, the primary objective of the present substudy is to assess the potential effects of plitidepsin at a therapeutic dose on the duration of the QTc interval, measured by continuous 12-lead ECG automated monitoring, in patients with COVID-19.

Secondary objectives are:

- To characterise the plitidepsin concentration/QTc relationship.
- To explore waveform morphology-related ECG parameters

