Sample Number	Day	Absolute Time (h) From the Start of First Plitidepsin Infusion	Time-points for Plitidepsin Samples (Time Window)
1	1	0	Just before first infusion
2	1	1	5 min before EOI (± 4 min)
3	1	2.5	1.5 h after EOI (± 15 min)
4	1	5	4.0 h after EOI (± 2 hour)
5	2	24	Just before Day 2 SOI (-15 to -1 min before SOI)
6	2	25	5 min before EOI (± 4 min)
7	2	26.5	1.5h after EOI (± 15 min)
8	2	29	4.0 h after EOI (± 2 hour)
9	3	48	Just before Day SOI (-15 to -1 min before SOI)
10	3	49	Just before EOI (± 4 min)
11	4	72	23 h after EOI (± 4 h)

Abbreviations: EOI = end of infusion; h = hour; SOI = start of infusion

Samples for the measurement of plitidepsin will have a volume of 2 mL. The exact recording of the time of drug administration and sampling times is crucial on treatment days with PK sampling (and should be noted accurately even if not according to the planned time schedule). The infusion rate of plitidepsin will be established to ensure that the total dose is infused in 1 hour. The drug will be infused at a constant rate throughout the 1-hour period. To obtain reliable PK information, the infusion rate should not be modified once the infusion begins. If a variation in the infusion time does occur, it is important to reflect this in the eCRF, clearly writing the time of the beginning and the end of the infusion. The infusion rate should not be changed to maintain the scheduled duration of infusion. It would be enough to record the actual duration in the eCRF and on the PK sampling sheet.

Blood samples for PK will be obtained through a peripheral vein located in the contralateral side to that of administration of plitidepsin. In any case, the sampling vein has to be different from that in which drugs are administered. The last sample must never be collected from the catheter used for the drug administration.

If the blood sample is obtained from a catheter, the first millilitre (mL) of blood will be discarded to avoid the dilution of the sample with the solution used to keep it clean. Heparin (10 U/mL in normal saline solution) or a slow drip of normal saline solution (10 mL/h) can be used to keep the catheter permeable between extractions.

Samples should be collected in a sodium heparin tube and gently inverted several times to ensure proper mixing. After sampling, the test tubes containing the blood samples will be immediately frozen until analysis. Samples are NOT to be centrifuged.

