Once all samples from a patient have been collected, they should be shipped to the designated laboratory as soon as possible, ideally the next shipping day. If the same centre has samples from several patients, samples can be sent in the same shipment. However, the time span between the moment the last PK sample for a patient has been

collected and the shipment of all samples from this patient to the laboratory should not exceed 2 months.

A manual of full instructions for sample extraction, labelling, storage, and shipment will be provided as a separate document.

ECG Evaluations

12-lead ECG Acquisition

The ECGs will be obtained digitally using a Mortara Instrument (Milwaukee, WI, USA) H-12+ECG continuous 12-lead digital recorder, which will obtain ECGs on Day 1 through Day 3. The ECGs will be stored continuously on a flash card and will not be available for review until the card is received by the emergency response team (ERT) and analysed. The patient's unique identification number and demographic information will be recorded for each card.

Patients will wear the continuous ECG recorder (Holter) from Days 1 to 3 (24 hours after end of infusion of Day 2). This ECG recorder will be provided by ERT after the study site has registered online at ERT's MYSTUDY PORTAL™. Registration details will be provided to the site coordinator at each participating site.

The ECG recorder will be set in place once all safety assessments scheduled for the main study (i.e., vital signs, blood sample extraction for laboratory tests, and ECG) have been conducted.

In this QT substudy, using pretreatment ECGs as the baseline and individual heart rate QT-correction, the Holter will be started, ideally, no less than 3 hours prior to the start of infusion of Day 1 through approximately 24 hours after the end of infusion of Day 2 (until the end of infusion on Day 3).

ECG Analysis Methods

All digital continuous ECG recordings will be sent to a third-party, central ECG laboratory ERT. The ECG readers will be blinded to patient identifiers and visit. All ECGs for a given patient will be analysed by the same reader. Quality Assurance reports for inter- and intra-observer variability will be produced by the central ECG laboratory and provided to the sponsor.

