Serial ECGs with stable resting heart rate will be extracted from the continuous recording in triplicate (three 10-second digital ECGs in close succession) as close as possible to the following timepoints relative to Day 1 and Day 2: 5 minutes before the EOI (time-matched to PK sample #2 and #6, respectively), 1.5 (time-matched to PK sample #3 and #7), 4 (time-matched to PK sample #4 and #8), and 23 hours (time-matched to PK sample #5, and #9) after EOI. On Day 1, 2 sets (triplicate) of baseline ECGs; prophylaxis (Predose 1) and postprophylaxis and before start of infusion (SOI) (Predose 2; time-matched to PK sample #1).

For the individual QT-RR correction (QTcI), low confidence beats from the continuous ECG recording will be reviewed using a pass-fail criterion.

Interval duration measurements will be collected using computer assisted caliper placements on 3 consecutive beats. Trained analysts will then review all ECGs for correct lead and beat placement and will adjudicate the preplaced algorithm calipers as necessary using the proprietary validated electronic caliper system applied on a computer screen. A cardiologist will then verify the interval durations and perform the morphology analysis, noting any T-U wave complex that is compatible with an effect on cardiac repolarisation.

The ECG analysis will be conducted in Lead II, or in Lead V5 if Lead II is not analysable. If Lead V5 is not analysable, then Lead V2 will be used followed by the most appropriate lead, if necessary.

On-screen measurements of the RR, PR, QRS, and QT interval durations will be performed and variables for QTcF and heart rate will be obtained by the following processes:

- Three (3) RR, PR, QRS and QT will be measured and mean RR interval, PR interval, QRS width and QT interval will be reported
- The following calculations will be made from the interval measurements:

Three (3) QTcF measurements (QTc correction by Fridericia)	Three (3) HR measurements
$QTcF1 = QT1/3\sqrt{RR1}$	$HR1 = 60/RR1$
$QTcF2 = QT2/3\sqrt{RR2}$	$HR2 = 60/RR2$
$QTcF3 = QT3/3\sqrt{RR3}$	$HR3 = 60/RR3$
Mean QTcF = $(QTcF1+QTcF2+QTcF3)/3$	Mean HR = $(HR1+HR2+HR3)/3$

Abbreviations: HR = heart rate; QTcF = QT interval corrected using Fridericia's formula

Each fiducial point (onset of P wave, onset of Q wave, offset of S wave, and offset of T wave) will be marked electronically. The original ECG waveform and such annotations will be saved separately in XML format for independent review.

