To enable an adequate comparison of the model fit between the direct and the indirect model, the model based predicted total plasma concentrations at central compartment (direct model) and at the effect compartment (indirect model) will be used.

Main Analysis

The relationship between total plasma concentration and ΔQTc will be assessed using a linear mixed effects (LME) model, as proposed by Garnett et al.¹¹ As the data available

come from a single arm study, the LME model will be characterised by the intercept (θ_1) and the slope (θ_2), and their corresponding variability (Equation 1, as below):

$$\Delta QTcF_{ij} = (\theta_1 \cdot e^{\eta_{1,i}}) + (\theta_2 \cdot e^{\eta_{2,i}}) \cdot C_{ij} + \theta_3 \cdot Day + e_{ij} \quad \text{Equation 1}$$

Where C_{ij} is the model-predicted plitidepsin total whole blood (observed) and or plasma (model-based estimated, as sensitivity analysis) concentrations (or the plitidepsin-concentrations in the effect compartment if a hysteresis is present), and $\eta_{1,i}$ and $\eta_{2,i}$ are the random effects associated with the intercept term θ_1 and the slope term θ_2 , respectively, and are assumed to be exponential, independent and normally distributed. Furthermore, e_{ij} is the random residual variability, assumed to be an additive, independent, and normally distributed random variable. In the absence of placebo data, the unstructured placebo model consisting on the fixed effect parameters accounting for treatment-specific intercept (TRT), mean QTc change from baseline at each timepoint evaluated ($TIME$), and baseline QTc, will not be included in the model. The model-based prediction of the total plasma concentrations will be based on the individual PK parameters, obtained through a maximum *a posteriori* estimation based on the individual total plasma concentration available for each subject and a population PK model of plitidepsin, previously developed.¹² Based on the fact that ECG assessments in this study will be performed on 2 occasions (Days 1 and 2), the effect of Day θ_3 will also be assessed in the models.

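### The QTc substudy is framed on three daily doses, but none of its eight post-dose ECG timepoints observes the third dose

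*Protocol*

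**What the plan says.** All of this is in protocol Appendix 8 (Protocol for QTc Substudy).

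- **Aim (Introduction).** The substudy "will determine whether plitidepsin at 1.5 and 2.5 mg flat dose on Days 1 to 3 has any effects on the QT interval".
- **ECG extraction (ECG Analysis Methods).** Triplicates are taken from the continuous recording at the "following timepoints relative to Day 1 and Day 2: 5 minutes before the EOI", then 1.5, 4 and 23 hours after the end of infusion (EOI), matched to PK samples 2 to 9. The last one is at "23 hours (time-matched to PK sample #5, and #9) after EOI".
- **Model (Main Analysis under C-ΔQTc).** The Day effect is included because "ECG assessments in this study will be performed on 2 occasions (Days 1 and 2").
- **Recording (12-lead ECG Acquisition).** The Holter runs from before the Day 1 infusion "through approximately 24 hours after the end of infusion of Day 2 (until the end of infusion on Day 3").
- **Blood (Table 6).** Sample 10 is on Day 3 at 49 h, timed "Just before EOI (± 4 min").
- **Pairing (Substudy Design Rationale).** "Samples for whole blood plitidepsin concentration measurement will be collected matching the clock times of ECG measurements".
- **Decision rule (Primary Analysis).** Non-inferiority requires the one-sided 95% upper bound of mean ΔQTc to be under 20 msec at every ECG timepoint.

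**The concern.** The regimen has three infusions and therefore three end-of-infusion peaks, marked by PK samples 2, 6 and 10. The by-timepoint test uses the first two. The concentration-QTc model has a Day term, but it has no observation made during or after the third infusion. A reader of the results would see a 20 msec conclusion attached to a question about three days of dosing, when the evidence covers two doses and the trough before the third.

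The omission is notable because the two ingredients of the missing pair are already planned: a recording that should reach the end of the third infusion, and a blood sample at that moment. Appendix 8 gives no reason for recording and sampling up to that point without reading an ECG there.

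**Working it through.** **1. The clock.** Table 6 counts hours from the start of the first infusion. Infusions last 1 hour and start nominally at 0, 24 and 48 h, so EOI falls at 1, 25 and 49 h.

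| Event | Arithmetic | Time (h) |
|---|---|---|
| ECGs relative to Day 1 | 1 − 5/60; 1 + 1.5; 1 + 4; 1 + 23 | 0.92; 2.5; 5; 24 |
| ECGs relative to Day 2 | 25 − 5/60; 25 + 1.5; 25 + 4; 25 + 23 | 24.92; 26.5; 29; 48 |
| Third infusion | – | 48 to 49 |
| Planned Holter end | 25 + 24 | 49 |
| PK sample 10 | Table 6 | 49 |
| Point that could be added | 49 − 5/60 | 48.92 |

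Post-dose ECG timepoints: 4 × 2 = 8. The latest is at 48 h, paired with sample 9, which is drawn before the third infusion starts. Timepoints after the start of dose 3: 0 of 8.

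**2. Is the recording assured at 48.92 h?** Only if the end-of-Day-3-infusion wording governs. Suppose the recorder comes off exactly 24 h after the Day 2 EOI, and the Day 3 infusion starts *d* minutes later than 24 h after the Day 2 start. The new ECG then falls *d* − 5 minutes after removal, so it is lost when *d* exceeds 5. Section 7.4.2.1 allows a 30 (±5) minute window for each day's infusion.

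**3. The plan's own sample size.** Inputs from Appendix 8, Sample Size: SD 30 msec, true change 5 msec, margin 20 msec, one-sided 5%, power 80%. For a single-group change from baseline:

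n = [SD × (z₀.₉₅ + z₀.₈₀) / (margin − true change)]² = [30 × (1.645 + 0.842) / 15]² = 24.73, rounded up to 25.

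This reproduces the stated 25. It is a per-timepoint figure, so a ninth timepoint leaves it unchanged. Because every timepoint must pass, no alpha adjustment is needed either.

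**4. What a ninth timepoint costs.** Pass probability at one timepoint, normal approximation: Φ(15/(30/√n) − 1.645).

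- n = 25: Φ(2.500 − 1.645) = 0.804
- n = 50: Φ(3.536 − 1.645) = 0.971

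Probability that all timepoints pass, with a true change of 5 msec at each and an assumed common correlation between timepoint estimates (simulation, 400,000 draws):

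| Evaluable patients | Correlation | 8 timepoints | 9 timepoints |
|---|---|---|---|
| 50 | 0 | 0.789 | 0.765 |
| 50 | 0.3 | 0.827 | 0.809 |
| 50 | 0.5 | 0.857 | 0.847 |
| 50 | 0.8 | 0.909 | 0.905 |
| 25 | 0 | 0.175 | 0.140 |
| 25 | 0.3 | 0.332 | 0.303 |
| 25 | 0.5 | 0.430 | 0.410 |
| 25 | 0.8 | 0.594 | 0.582 |

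Both sizes are shown because Appendix 8 gives 25 in its sample size section and 50 as its enrolment target. The documents give no correlation, so the column is a range of assumptions.

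**The case against.** The best defence is that this is a deliberate two-occasion design. ECG Analysis Methods and the model section agree on Days 1 and 2. The aim can be read as naming the regimen rather than promising a result for each dose, and the formal objective speaks only of a therapeutic dose. The Endpoint definition does refer to post-dose timepoints on Days 1 to 3, but the 48 h ECG satisfies that literally, since Table 6 lists its paired sample under Day 3. This stands: no stated figure is wrong, and the sections do not flatly contradict each other.

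The protocol also supplies mitigation. Section 3.4 states that accumulation over three daily doses is minimal, although this comes from a simulation in typical subjects with a 1.5-hour infusion, while this trial infuses over 60 minutes. The main study takes a triplicate ECG after the Day 3 infusion (Section 7.4.2.1 and Appendix 5). Section 8.7 summarises it descriptively, and it lies outside the substudy's centrally read test and model. These points lower the consequence but leave the substudy without evidence on dose 3.

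A reader might infer three stronger things that the documents do not support:

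- **That a delayed effect of dose 3 is missed and the extra ECG would catch it.** A point 5 minutes before EOI precedes any post-infusion delay. Hysteresis is addressed by the ECGs at 1.5, 4 and 23 hours after doses 1 and 2. Later dose 3 points would need a longer recording.
- **That Day 3 data are thrown away.** Sample 10 still serves the substudy's PK objective and can inform the individual PK parameters. Only its ECG pair is missing.
- **That a strict pairing rule is broken.** Sample 11, at 72 h, also has no ECG and falls after the Holter ends, so the pairing sentence cannot mean that every sample has one.

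**Conclusion.** The gap is real and of moderate weight. The by-timepoint non-inferiority conclusion and the concentration-QTc model, as planned, rest on two of the three doses, while the substudy is introduced as addressing dosing on Days 1 to 3. One of three end-of-infusion peaks goes unread.

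The documents do not show that the third peak is higher or its QTc effect larger. With minimal accumulation it may resemble the second. The point is that the substudy would not show this, although it could at little cost.

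The timing rests on the nominal Table 6 clock and on the recorder staying on to the Day 3 EOI. The cost of a ninth timepoint rests on the plan's SD and true change and on the assumed correlations. With 50 patients the joint pass probability drops by 0.004 to 0.024 over the range shown.

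**What to change.** In Appendix 8:

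1. Add one triplicate extraction about 5 minutes before the Day 3 EOI, time-matched to PK sample 10, and use the same timing words for the ECG and the sample.
2. Make the end of the Day 3 infusion the governing Holter end time, so that a later Day 3 start does not lose the point.
3. Carry it as a ninth timepoint in the by-timepoint, categorical and concentration-QTc analyses. Give the Day effect three levels, indexed by infusion, rather than a single linear step. The third level would rest on one ECG time per patient, so it can show a shift on Day 3 but not a separate slope.
4. Amend the sentence that describes two ECG occasions.

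If the extraction is not added, state that the non-inferiority conclusion covers the first two doses only.

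The cost is one more central reading per substudy patient from a planned recording, with no new visit, blood draw or change in sample size. The downside is the slightly harder joint criterion (0.857 to 0.847 in the 50-patient, correlation 0.5 case). Restricting the conclusion costs only wording.

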For the triplicate ECGs collected at each timepoint, the average of the 3 measurements for each ECG parameter will be considered for all listing and statistical analyses described below.

Investigators are not expected to evaluate or otherwise assess the ECGs unless alerted by the central ECG laboratory to the possibility of a clinically relevant reading.

QT Correction Methods

The QT will be corrected for heart rate using the following methods:

- QTcF³
- Estimation of the exponent at an individual level (QTcI)⁹

The most appropriate method, based on the lack of statistical significance of the slope between QTc and heart rate, will be used for the concentration-QTc analysis.

Endpoint definition

In principle, for each patient and each postdose timepoint on Days 1 to 3, baseline QTc intervals will be the mean of the predose 1 and predose 2 QTc values for that patient on Day 1.

If the mean predose 2 QTc value of all evaluable patients is ≥ 10 msec longer than of the mean predose 1 QTc value, an effect of prophylactic medication on QTc cannot be ruled out; therefore, individual predose 2 QTc values will be considered as the baseline values.

The change from baseline (Δ QTc) will be calculated using the corresponding baseline QTc values. Specifically:

- Δ QTc at time t: Difference in QTc between scheduled timepoint t and baseline.

The primary endpoint will be Δ QTc at each scheduled timepoint.

STATISTICAL METHODS

Sample Size

Assuming that the intrasubject standard deviation for change from baseline in QTc (Δ QTc) is 30 msec and that the true difference between means is 5 msec, a sample size of at least 25 evaluable patients in more than 80% of the scheduled ECG timepoints t is planned to have 80% power to show that the upper limit of the 2-sided 90% confidence interval (CI; 1-sided upper 95% CI) for mean Δ QTc at each ECG timepoint t is < 20 msec.

Primary Analysis

“By Timepoint” Analysis

The primary objective of this QT evaluation study is to measure the potential effect of plitidepsin on QTc. The primary comparison of interest is Δ QTc at each ECG timepoint t. A noninferiority criterion of 20 msec will be used to establish that postbaseline QTc is noninferior to baseline.

An analysis of variance model (ANOVA) with mixed effects will be fitted, with Δ QTc data as the dependent variable and ECG timepoint t as the fixed effects, and patient as random effect.

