Using the estimated least square means (LSM) and intrapatient standard deviation obtained from this model, a 2-sided 90% CI will be calculated for each LSM Δ QTc. Noninferiority will be concluded if the upper bound of the 1-sided 95% CI falls below 20 msec at each ECG timepoint.

Mean QTc and corresponding changes from baseline (Δ QTc) will be listed and summarised descriptively by ECG timepoint. Plots of mean Δ QTc *versus* ECG timepoint will be prepared.

Categorical Analysis

Categorical (or outlier) reference limits will be defined in terms of change from baseline values or as absolute values, according to the ICH E14 guidance.

The incidence counts and percentage of patients with $\Delta QTc \leq 30$ msec, ΔQTc 30 to 60 msec and $\Delta QTc > 60$ msec will be tabulated for each ECG timepoint t and described for age and gender.

The incidence counts and percentage of patients with any new postbaseline QTc values > 450 msec, > 480 msec, and > 500 msec will be tabulated for each ECG timepoint t, and described for age and gender. Patients with new QT and QTc values > 500 msec will be listed.

Secondary Analyses

C- ΔQTc analysis

Exploratory Analysis

Before the model selection for the C- ΔQTc analysis, a potential delay of the ΔQTc effect relative to plasma concentrations (hysteresis) will be graphically and statistically assessed, as proposed by Darpo et al.¹⁰ Plots of the time course of mean plasma concentrations and mean ΔQTc will be overlaid, to allow detection of delay in the time to QTc peak relative to plasma concentrations. In addition, study data will be analysed to check whether any of the following 3 statistical criteria are met to conclude the presence of hysteresis:

1. Largest mean ΔQTc exceeding 5 msec at ≥ 3 timepoints
2. Time difference between U_{max} (the time of the largest mean ΔQTc) and T_{max} of plitidepsin exceeding 1 hour, and
3. One-sided 1-sample Wilcoxon test for the difference between ΔQTc at T_{max} and at U_{max} formally significant at the 1% level

If the presence of hysteresis is concluded, the primary analysis of the C- ΔQTc will be based on an effect compartment (“indirect”) model. However, if only some of the 3 criteria (not all) are met, the indirect model will be assessed and compared with a direct effect (“direct”) model and, consequently, the model that provides the best description of the available data will be used for the primary model based analysis of the C- ΔQTc .

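### QTc substudy: choosing QTcF or QTcI by a non-significant QTc–heart rate slope does not show that the residual slope is small, gives no answer when both or neither passes, and conflicts with Equation 1

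*Protocol*

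**What the plan says.** Appendix 8 of the protocol, under QT Correction Methods, lists two corrections: QTcF and an individual correction, QTcI, whose exponent is estimated for each patient. It then gives the selection rule: "The most appropriate method, based on the lack of statistical significance of the slope between QTc and heart rate, will be used". The sentence ends by limiting the rule's reach; the chosen method "will be used for the concentration-QTc analysis". That analysis stands under Secondary Analyses.

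The rule gives no significance level, no slope size that counts as adequate, no set of ECGs for the test, and no outcome when both or neither slope is significant.

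Three other places in Appendix 8 bear on it:

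- 12-lead ECG Acquisition describes the substudy as "using pretreatment ECGs as the baseline and individual heart rate QT-correction". This suggests, without saying so, that the QTcI exponents come from pretreatment recordings.
- Equation 1, the concentration-QTc model, has ΔQTcF on its left-hand side.
- Endpoint definition and Primary Analysis refer only to QTc and ΔQTc. They name no correction.

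**The concern.** The rule runs the inference the wrong way. Failing to reject a zero slope is read as showing that QTc is free of heart rate. Sparse or noisy data make that outcome more likely, so a poor correction can pass. Dense data can reject a correction whose residual slope is of little consequence. Because the data set is open, the same correction can be accepted or rejected according to a choice made after the recordings are in hand.

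Two further gaps add to this. If both corrections pass, or both fail, the rule selects nothing and the analyst decides. If QTcI is selected, Equation 1 as written cannot be the model that is fitted.

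At stake is the analysis relating plitidepsin concentration to QTc. The substudy enrols only patients randomised to plitidepsin, and the protocol notes that there are no placebo data, so no control group offsets an error in heart-rate correction.

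**Working it through.** **The plan's own figure.** Appendix 8 sizes the by-timepoint primary analysis. It assumes that the SD of ΔQTc "is 30 msec and that the true difference between means is 5 msec", with a 20 msec margin and a one-sided 95% bound:

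n = [30 × (1.645 + 0.842) / (20 − 5)]² = 24.7, rounded up to 25.

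The stated 25 reproduces. It does not size the slope test, for which the protocol gives no power.

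**How often a real residual slope is missed.** From the protocol: 50 evaluable patients targeted, 25 in the sample-size statement, and ten ECG timepoints (two predose, four after each of the first two infusions). Assumed: residual SD 15-25 msec, heart-rate SD 10-15 bpm, true residual slope 0.5 msec/bpm, two-sided 5% test, values treated as independent.

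SE = SD_QTc / (SD_HR × √M), where M is the number of values; miss rate = Φ(1.96 − 0.5/SE).

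| Values in the test | SD 15, HR SD 15 | SD 20, HR SD 12 | SD 25, HR SD 10 |
|---|---|---|---|
| 25 patients × 1 | SE 0.200, 29% | SE 0.333, 68% | SE 0.500, 83% |
| 50 patients × 1 | SE 0.141, 6% | SE 0.236, 44% | SE 0.354, 71% |
| 50 patients × 2 predose | SE 0.100, <1% | SE 0.167, 15% | SE 0.250, 48% |
| 50 patients × 10 timepoints | SE 0.045, <1% | SE 0.075, <1% | SE 0.112, <1% |

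With a narrower heart-rate spread of 5 bpm, the ten-timepoint test misses the slope 0%, 25% and 54% of the time at residual SD 10, 21.2 and 30 msec. In the other direction, at residual SD 10 msec and heart-rate SD 10 bpm, the ten-timepoint test finds a slope of only 0.2 msec/bpm non-significant just 1% of the time. It would therefore reject on that slope 99% of the time.

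**The same corrections on different data.** Simulation of 50 patients: true QT-RR exponent averaging 0.25 (so QTcF, with 1/3, is wrong), residual CV 5%, within-patient heart-rate SD 5 bpm, QTcI fitted on 60 predose Holter points per patient.

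| ECGs used for the slope test | QTcF passes | QTcI passes |
|---|---|---|
| Two predose ECGs | 86% | 95% |
| All ten timepoints | 37% | 96% |
| The 60 Holter points that fitted QTcI | 0% | 100% |

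Across the 50-patient scenarios at 5% CV, QTcI passed 89-96% of the time on ECGs separate from its fitting data. That is close to the pass rate of a correct method: QTcF passed 90-94% when the true exponent averaged 0.333.

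**The undefined case.** If two methods pass with probabilities p and q, both pass with probability at least p + q − 1. On two predose ECGs that is at least 0.86 + 0.95 − 1 = 81%; on all ten timepoints, at least 0.37 + 0.96 − 1 = 33%. In this scenario the rule gives no choice in most trials that test on predose ECGs, although QTcF is wrong.

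**Rule against model.** QT Correction Methods makes the correction for the concentration-QTc analysis depend on the data. Equation 1, the model for that analysis, fixes QTcF. Both hold only if the rule happens to select QTcF.

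**The case against.** The strongest reply is that weakness of the test is assumed. One value per patient is sparser than anything the substudy collects: there are ten timepoints and a continuous recording that should ideally start at least 3 hours before the first infusion. The table bears this out, with the miss rate below 1% on the same inputs once all ten timepoints enter. The enrolment target is about 50, so the 25-patient row is not the planned case. This stands, and no claim that the test is underpowered should be made. What remains is that the protocol does not say which ECGs are used, and on that the answer turns.

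A reader might also infer that QTcI passes by construction. The documents do not support that. It holds only if the slope is tested on the ECGs that fitted the exponents, and the protocol does not say so. Nor does it require separate ECGs.

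A third inference is that the primary QTc conclusion is in danger. With an assumed 10 bpm fall in heart rate on treatment, a 0.5 msec/bpm slope would shift ΔQTc by 5 msec, and simulated QTcF shifted it by −4.8 or +3.6 msec (true exponent 0.25 or 0.40). But the rule governs only the secondary analysis, and the primary one is judged against 20 msec, so setting this shift beside the 5 msec of the primary sample-size assumption is misplaced. In Equation 1 a gradual drift would fall largely on the intercept and the Day term. Only heart-rate change that tracks concentration biases the concentration slope, and no such bias has been calculated.

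Finally, the F in Equation 1 may be loose notation, and the significance level, test data and tie-break may be in the SAP, which is not at hand. Those details could be settled there. The criterion itself is fixed in the protocol, and it is the criterion that is unsound.

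**Conclusion.** The point holds as a badly fixed decision rule for a secondary safety analysis. Non-significance of the slope is the wrong criterion, the rule is silent when both or neither method passes, and Equation 1 conflicts with a choice made from the data. These three conclusions rest on the text alone.

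The size is illustrative. A residual slope of 0.5 msec/bpm is missed 6-71% of the time with one value from each of 50 patients (44% in the central case) and 29-83% with 25. The rate is near zero on the same inputs with all ten timepoints. The residual SD, heart-rate SD and slope are assumptions without support in the protocol, and treating repeated ECGs as independent overstates the information in the multi-ECG rows if patients differ systematically. The direction of the error cannot be derived from the document. The change is worth making, but the by-timepoint conclusion is not shown to be at risk.

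**What to change.** Replace the significance rule in QT Correction Methods by one of two options:

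1. Prespecify one correction for the concentration-QTc analysis, for example QTcF as in Equation 1, with the other as a sensitivity analysis.
2. Compute both and take the method with the smaller residual QTc-RR slope, reported with its 90% CI, on drug-free ECGs not used to fit the QTcI exponents. The predose Holter recording could be split for this.

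Either option removes the undefined case. In addition, name the correction used for ΔQTc in the by-timepoint primary analysis, and make the left-hand side of Equation 1 agree with the choice.

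The cost is wording in Appendix 8 and one sensitivity analysis. No further data are needed, because both corrections are already to be computed. Option 1 is simpler and leaves nothing to decide after the data are seen. Option 2 keeps the choice data-driven but uses part of the predose recording for assessment rather than fitting, which makes the individual exponents somewhat less precise.
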